## 5.5.2 Hematological dose limiting toxicity

### 5.5.2.1 **In patients evaluable for hematological toxicity (see [Section 11.2.1](#)), hematological dose limiting toxicity is defined as:**

Failure to recover a peripheral ANC > 200/ $\mu$ L and non-transfusion dependent platelets > 20,000/ $\mu$ L by 43 days after the first treatment day with fludarabine and cytarabine, not due to malignant infiltration (including MRD by central flow cytometry analysis) or  $\geq$ Grade 3 infection or sepsis. Failure to recover peripheral counts due to disease involvement of the bone marrow will not be considered dose-limiting.

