## 11.0 STATISTICAL AND ETHICAL CONSIDERATIONS

### 11.1 Sample Size and Study Duration

The study will require a minimum of 4 DLT-evaluable patients and a maximum of 12. Once the MTD or recommended Phase 2 dose has been defined, up to 6 additional patients with recurrent or refractory AML, t-AML, MDS, t-MDS or MPAL without restrictions on heme evaluability may be enrolled to acquire PK data in a representative number of young patients so that the study includes an approximately equal distribution of patients <12 years old and 12-17 years old. Therefore, the expected maximum number of patients required for the entire study will be 22 allowing for 6 evaluable patients at each of two dose levels, 20% inevaluability for DLT or for failure to contribute essential PK samples (for patients with weight  $\geq 10$  kg: pre-dose, 30 minutes and 2 hrs after the dose on days 1 and 6; for patients with weight <10 kg: pre-dose, 30 minutes and 1.5 hrs after the dose on days 1 and 6), and 6 additional patients for PK analysis at the MTD/RP2D. The absolute maximum will be 36 patients which would occur in the unlikely scenario that both dose levels expand to 12 due to DLTs of different classes (See [Section 11.2.2](#)).

The enrollment rate is expected to be about 1 patient per month based on previous COG early phase new agent studies for patients with AML. Therefore, the study may require up to 36 months to complete enrollment but is expected to be completed within about 22 months.

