### 11.2 Definitions

#### 11.2.1 Evaluable for Adverse Events

Any patient who receives at least one dose of the study drugs is considered evaluable for Adverse Events. In addition, for the dose-escalation portion during Cycle 1, patients must receive at least 85% of the prescribed dose per protocol guidelines and must have the appropriate toxicity monitoring studies performed to be considered evaluable for dose limiting toxicity. Patients in the dose escalation part of the study, who do not have DLT and are not considered evaluable for toxicity will be replaced.

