#### 11.2.2 Maximum Tolerated Dose

- The MTD will be the maximum dose at which fewer than one-third of patients experience DLT (See [Section 5.5](#)) during Cycle 1 of therapy.
- In the unlikely event that two DLTs observed out of 6 evaluable patients are different classes of Adverse Effects (eg, hepatotoxicity and myelosuppression), AND all of the following conditions are met, expansion of the cohort to 12 patients will be considered:
  - One of the DLTs does not appear to be dose-related
  - The Adverse Effects are readily reversible
  - The study chair, PEP-CTN statistician, PEP-CTN committee chair or vice chair, and IND sponsor all agree that expansion of the cohort is acceptable
- The DLTs observed in the pharmacokinetic (PK) expansion cohort will be counted towards the total number of DLTs observed at the MTD. If  $\geq 1/3$  of the cohort of patients at the MTD (during the dose evaluation plus the PK expansion) experience DLT then the MTD will be exceeded.

THIS PROTOCOL IS FOR RESEARCH PURPOSES ONLY, SEE PAGE 1 FOR USAGE POLICY

- If the maximum dose level (DL1) is safe (i.e., less than 1/3 of patients experience a Cycle 1 DLT among 6 DLT-evaluable patients), then DL1 will be the RP2D.
- Patients enrolled in the PK expansion cohort will be replaced if unevaluable for PK analysis defined as pre-dose, 30 minutes and 2 hrs after the dose on days 1 and 6 for patients with weight  $\geq 10$  kg; pre-dose, 30 minutes and 1.5 hrs after the dose on days 1 and 6 for patients with weight  $<10$  kg

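### The pooled Part A plus Part B one-third DLT rule counts Part B patients who need not meet any DLT-evaluability criterion, and the definition of hematological evaluability is missing

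*Combined protocol and SAP*

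**What the plan says.** - **Section 5.5.2.1** introduces hematological DLT with "In patients evaluable for hematological toxicity" and refers to Section 11.2.1. The event is failure of counts to recover by 43 days after the first fludarabine and cytarabine treatment day, "not due to malignant infiltration (including MRD by central flow cytometry analysis") or to serious infection. It adds: "Failure to recover peripheral counts due to disease involvement of the bone marrow will not be considered dose-limiting".
- **Section 11.2.1** makes anyone who received a dose evaluable for adverse events. For DLT it adds that "for the dose-escalation portion during Cycle 1, patients must receive at least 85% of the prescribed dose per protocol guidelines" and must have had the toxicity monitoring. On replacement: "Patients in the dose escalation part of the study, who do not have DLT and are not considered evaluable for toxicity will be replaced". It has no category of hematological evaluability.
- **Section 11.1** says the up to six Part B patients "without restrictions on heme evaluability may be enrolled to acquire PK data in a representative number of young patients".
- **Section 11.2.2** counts Part B DLTs toward the total. The MTD is exceeded if one-third or more "of the cohort of patients at the MTD (during the dose evaluation plus the PK expansion) experience DLT". Part B patients are replaced only if essential PK samples from Days 1 and 6 are missing.
- **Section 11.3** words the Part A decision in terms of DLT-evaluable patients. For the combined check it drops that qualifier, counts patients in both parts, and sets the trigger at more than 33%.

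**The concern.** The numerator and denominator of the pooled rule come from different populations. A Part A patient without a DLT who missed too much drug or monitoring is removed and replaced. A Part B patient in the same position stays in as DLT-free. Such a patient can lower the pooled rate but never raise it, so the bias is toward a lower rate.

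The pooled check is what can overturn the recommended dose after Part A has passed, so the dilution acts on the primary safety decision. The missing definition compounds this: two people applying Section 5.5.2.1 could disagree on who is able to have a hematological DLT, and neither could settle it from the text.

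**Working it through.** **The plan's own figures.** Section 11.1 gives 22 expected and 36 absolute maximum. (6 + 6 + 6) × 1.2 = 21.6, rounded up to 22; (12 + 12 + 6) × 1.2 = 36. Both reproduce and neither is affected by this point. The plan states no DLT rate and no operating characteristics for the one-third rule.

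**Can a Part B patient be PK-evaluable but fall short of the Part A dose criterion?** The schedule in Section 5.1.1 is one uproleselan dose on Day 1 and two per day on Days 2 to 8, 15 in all. Day 6 PK sampling follows the first dose of that day: 1 + 4 × 2 + 1 = 10 doses, and 10/15 = 67%. If the 85% criterion is read as applying to uproleselan, it needs 0.85 × 15 = 12.75, that is 13 doses. So the answer is yes.

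**When does dilution change the decision?** Take 12 patients at the dose, six per part, with inevaluable patients in Part B and without a DLT. Both triggers (at least one-third, and more than 33%) need the same number of DLTs here:

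| Evaluable patients | DLTs that trip the rule | One DLT fewer gives |
|---|---|---|
| 12 | 4 (33.3%) | 3/12 = 25.0% |
| 11 | 4 (36.4%) | 3/11 = 27.3% |
| 10 | 4 (40.0%) | 3/10 = 30.0% |
| 9 | 3 (33.3%) | 2/9 = 22.2% |

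With one or two inevaluable, the trigger stays at 4 and the decision is the same. With three, 3 DLTs exceed the limit over 9 patients but not over 12.

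**How often?** Assumptions: true DLT rate p (not given in the documents, so shown as a range); X ~ Bin(6, p) in Part A; Part B opens if X ≤ 1; three Part B patients are evaluable, Y ~ Bin(3, p); the other three contribute no DLT.

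- All 12 in the denominator: trips if X + Y ≥ 4, which needs X = 1 and Y = 3.
- The 9 evaluable: trips if X + Y ≥ 3.

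At p = 0.40: P(X=0) = 0.6⁶ = 0.0467 and P(X=1) = 6 × 0.4 × 0.6⁵ = 0.1866, so Part A passes with probability 0.2333, and given that, X is 0 or 1 with probability 0.2 or 0.8. P(Y=3) = 0.064; P(Y≥2) = 0.352.

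- Over 12: 0.8 × 0.064 = 0.051.
- Over 9: 0.8 × 0.352 + 0.2 × 0.064 = 0.294.

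| True DLT rate | Part A passes | Trips over 12, three inevaluable | Trips over the 9 evaluable | Trips if all 12 were evaluable |
|---|---|---|---|---|
| 25% | 53.4% | 1.0% | 10.9% | 12.5% |
| 33% | 35.8% | 2.7% | 19.9% | 25.8% |
| 40% | 23.3% | 5.1% | 29.4% | 40.0% |
| 50% | 10.9% | 10.7% | 44.6% | 61.2% |

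The three right-hand columns are conditional on Part A having passed. Unconditionally, at 40% the dose is kept with probability 0.2333 × (1 − 0.0512) = 22.1% over 12, against 0.2333 × (1 − 0.2944) = 16.5% over the 9.

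**Timing of the hematological assessment.** Chemotherapy starts on Day 2, so 43 days later is Day 45. Section 5.5 makes the DLT window the first cycle, defined as 28 days. The last uproleselan dose is on Day 8, so the Section 10.2 off-study point after one cycle is Day 8 + 30 = Day 38. A one-cycle patient can leave the study before the event can be judged.

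**The case against.** Much of the case on the other side stands.

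- **Part B is not without control.** It has a PK-evaluability rule with replacement. The Table 8 observations are not limited to Part A, and Section 10.1 continues Cycle 1 observations after removal from therapy. What is missing is a DLT-evaluability rule.
- **The Part A gate already does most of the work.** It uses DLT-evaluable patients and stops at 2 of 6. A pooled flip needs at least three inevaluable Part B patients, which may not happen.

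Four stronger readings are tempting, but the documents do not support them.

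1. *That a single inevaluable Part B patient reverses the decision.* In a fixed cohort of 12 this does not happen. It would take a 13th patient (4/12 = 33.3% against 4/13 = 30.8%), arising if a replaced PK-inevaluable patient still counts for DLT. The documents do not say whether that patient counts.
2. *That patients whose leukemia persists are counted as DLT-free among the six in Part A.* Section 11.3 counts DLT-evaluable patients, and lifting the hematological restriction for Part B implies one was meant in Part A. The Part A fault is a missing definition.
3. *That remission rates show how many patients could have a hematological DLT.* COG-CR and COG-CRi in Appendix VIII require count recovery at or above the thresholds whose failure is the DLT. A leukemia-free patient with prolonged aplasia is largely outside the responder count, and the documents give no aplasia rate.
4. *That a patient inevaluable for hematological toxicity could never show a DLT.* Non-hematological DLTs still count for that patient.

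**Conclusion.** The concern holds for the pooled check. Followed as written, Sections 11.2.2 and 11.3 can keep a dose that the same one-third limit would reject among evaluable patients: 3/12 = 25.0% against 3/9 = 33.3%. With three inevaluable Part B patients and true DLT rates of 33% to 50%, the chance of tripping after Part A has passed is 2.7% to 10.7% instead of 19.9% to 44.6%. These figures rest on an assumed DLT rate and an assumed number of inevaluable patients. With one or two inevaluable among 12, only the reported rate is diluted.

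The absent definition of hematological evaluability is a separate, certain gap. Patients unable to show a hematological DLT can only lower the rate, but the size of that bias cannot be derived from the documents.

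The point should be corrected; it does not invalidate the design.

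**What to change.** 1. **Pooled denominator.** In Sections 11.2.2 and 11.3, restrict the combined Part A and Part B denominator to patients who had a Cycle 1 DLT or met the Section 11.2.1 dose and monitoring criteria. Extend those criteria to Part B for this purpose.
2. **Hematological evaluability.** Define it in Section 11.2.1: the marrow finding required, the count follow-up required, and the handling of patients who start other therapy first. Report hematological DLTs over that group, separately from non-hematological DLTs. No new stopping rule is needed: any two DLTs among six already exceed the limit in Part A, so a separate hematological limit requiring two events would add nothing there.
3. **Timing.** Reconcile the 43-day hematological assessment (Section 5.5.2.1) with the first-cycle DLT window (Section 5.5) and the off-study point 30 days after the last dose (Section 10.2).

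**Cost.** Items 1 and 2 are wording and need no added enrollment. Item 3 may mean collecting counts for longer in one-cycle patients, depending on how it is resolved. The denominator becomes smaller and the reported DLT rate may look slightly worse. A tolerable dose is also dropped a little more often: at a true rate of 25% with three inevaluable, the chance of keeping it falls from 0.534 × (1 − 0.010) = 52.8% to 0.534 × (1 − 0.109) = 47.6%, close to the 46.7% that applies if all 12 were evaluable (0.534 × (1 − 0.125)).

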### 5.5.2.2 **Note:** Grade 3 or 4 febrile neutropenia will not be considered a dose-limiting toxicity.

## 5.6: THERAPY DELIVERY MAPS (TDMS) FOR CYCLE 1-2

**Therapy Delivery Map – Cycle 1-2** A cycle of therapy is considered to be 28 days. A cycle may be repeated for a total of 2 cycles, up to a total duration of therapy of approximately 2 months. Refer to [section 4.1](#) for eligibility criteria to start cycle 1. For patients in MRD negative remission, it is required that patients have an ANC >200/ $\mu$ L or a sustained platelet count >20,000/ $\mu$ L before proceeding with cycle 2.

This form is to be completed and uploaded into RAVE at the end of every cycle.

Accession #

Patient COG ID number

Institution

Extensive details are in [Section 5.1](#) (treatment overview). This TDM extends to three pages.

DRUG	ROUTE	DOSAGE	DAYS	IMPORTANT NOTES																				
IT Cytarabine (AraC)	Intrathecal (IT)	Age-based dosing: 

Age	Dose	

< 1 year	20 mg	

≥ 1 to < 2 years	30 mg	

≥ 2 to < 3 years	50 mg	

≥ 3 years	70 mg	

	Age	Dose	< 1 year	20 mg	≥ 1 to < 2 years	30 mg	≥ 2 to < 3 years	50 mg	≥ 3 years	70 mg	Days 0 ^ , 7*, 14*, 21*, 28 ^	
^All patients. First time point given at the time of diagnostic lumbar puncture OR Day 0 for all patients. Note that Day 28 LP with IT chemotherapy of Cycle 1 counts as Day 0 LP with IT of Cycle 2. If the patient received IT cytarabine or triple IT therapy during their diagnostic workup within 14 days of starting protocol therapy, then they do not need additional Day 0 IT therapy.
 
*CNS 2/3 patients ONLY.
 
A minimum of 4 and a maximum of 6 weekly (count includes day 0 IT) intrathecal treatments may be given. The choice between IT Cytarabine OR IT Triples is up to the treating physician's discretion. See Section 5.1 for administration guidelines.
										
Age	Dose																							
< 1 year	20 mg																							
≥ 1 to < 2 years	30 mg																							
≥ 2 to < 3 years	50 mg																							
≥ 3 years	70 mg																							
IT Triples (Methotrexate [MTX], Hydrocortisone [HC], Cytarabine [AraC]) (ITT)	IT	Age-based dosing: 

Age	MTX	HC	ARAC	

< 1 year	6 mg	12 mg	18 mg	

≥ 1 to < 2 years	8 mg	16 mg	24 mg	

≥ 2 to < 3 years	10 mg	20 mg	30 mg	

≥ 3 years	12 mg	24 mg	36 mg	

	Age	MTX	HC	ARAC	< 1 year	6 mg	12 mg	18 mg	≥ 1 to < 2 years	8 mg	16 mg	24 mg	≥ 2 to < 3 years	10 mg	20 mg	30 mg	≥ 3 years	12 mg	24 mg	36 mg	Days 0 ^ , 7*, 14*, 21*, 28 ^	
^All patients. First time point given at the time of diagnostic lumbar puncture OR Day 0 for all patients. Note that Day 28 LP with IT chemotherapy of Cycle 1 counts as Day 0 LP with IT of Cycle 2. If the patient received IT cytarabine or triple IT therapy during their diagnostic workup within 14 days of starting protocol therapy, then they do not need additional Day 0 IT therapy.
 
*CNS 2/3 patients ONLY.
 
A minimum of 4 and a maximum of 6 weekly (count includes day 0 IT) intrathecal treatments may be given. The choice between IT Cytarabine OR IT Triples is up to the treating physician's discretion. See Section 5.1 for administration guidelines.

Age	MTX	HC	ARAC																					
< 1 year	6 mg	12 mg	18 mg																					
≥ 1 to < 2 years	8 mg	16 mg	24 mg																					
≥ 2 to < 3 years	10 mg	20 mg	30 mg																					
≥ 3 years	12 mg	24 mg	36 mg																					
Leucovorin (LCV) %	PO or IV	5 mg/m  /dose q6hr x 2 doses	1, 8, 15, 22, 29	
% Down-syndrome patients who are receiving ITT ONLY. Administer 24 & 30 hours after each IT Triples dose.
 
See Section 5.1 for administration guidelines.
																				
Uproleselan (GMI-1271) IND# 139758	IV over 20 minutes ±2 min.	Day 1: 10 mg/kg x 1 dose  Days 2-8: 10 mg/kg Q12H	1, 2-8	
Day 1: Administer 24 hours ±2 hours prior to the first dose of Fludarabine.
 
Days 2-8: Administer every 12 hours ±1 hour starting 2 hours ±15 minutes prior to initiation of Fludarabine.
 
Total number of doses: 15
																				
Fludarabine (FLU)	IV over 30 minutes	Age-based dosing: 

Age (yrs)	Dose	

< 1	1 mg/kg/dose once daily	

≥ 1	30 mg/m^2/dose once daily	

	Age (yrs)	Dose	< 1	1 mg/kg/dose once daily	≥ 1	30 mg/m  /dose once daily	2-6															
Age (yrs)	Dose																							
< 1	1 mg/kg/dose once daily																							
≥ 1	30 mg/m  /dose once daily																							
Cytarabine (HD ARAC)	IV over 1-3 hours	Age-based dosing: 

Age (yrs)	Dose	

< 1	67 mg/kg/dose once daily	

	Age (yrs)	Dose	< 1	67 mg/kg/dose once daily	2-6	Begin administration 4 hours after the start of the fludarabine infusion.																
Age (yrs)	Dose																							
< 1	67 mg/kg/dose once daily																							

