## 5.3 **Dose Level Schema**

### 5.3.1 **Uproleselan (GMI-1271) Dosing:**

The starting dose will be 10 mg/kg with dose levels for subsequent groups of patients as follows.

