**Table 5 – Uproleselan Dose Level Schema**

Dose Level	Uproleselan (GMI-1271) dose
-1	5 mg/kg
1*	10 mg/kg

\*Starting dose level

A Dose Level 2 will only be considered after evaluation of PK and toxicity at Dose Level 1. If PK clearance is >30% compared to adults and if the MTD has not been reached at Dose Level 1, a Dose Level 2 will be considered.

If the MTD has been exceeded at the first dose level, then the subsequent cohort of patients will be treated at Dose Level -1. If Dose Level -1 is not well tolerated, further de-escalation will not occur. The study will be closed to accrual.

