### 6.1 Dose Modifications for Hematological Toxicity

6.1.1 Patients who experience a hematologic dose limiting toxicity defined as failure to recover a peripheral blood ANC > 200/ $\mu$ L and non-transfusion dependent platelet count > 20,000/ $\mu$ L by 43 days after the start of the cycle, not due to malignant infiltration or severe infection will be allowed to proceed to Cycle 2 at the next lower dose level at the discretion of the treating physician and study chair or vice-chair. If patient is starting at Dose Level -1, further de-escalation will not occur and the patient must be removed from protocol therapy.

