### 6.2 Dose Modifications for Non-Hematological Toxicity

6.2.1 Patients who have any dose-limiting non-hematological toxicity (as defined in [Section 5.5.1](#)) may continue on protocol therapy upon meeting eligibility lab requirements (see [Section 4.0](#)) or Grade  $\leq 2$  but should receive subsequent doses at the next lower dose level. If patient is starting at Dose Level -1, further de-escalation will not occur and the patient must be removed from protocol therapy.

6.2.2 If a non-hematological dose-limiting toxicity recurs after one dose reduction, the patient must be removed from protocol therapy.

6.2.3 Patients who have a dose-limiting non-hematological toxicity that does not resolve to Grade  $\leq 2$  or eligibility within 43 days after the start of the cycle, must be removed from protocol therapy.

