### 11.3 Dose Evaluation and Determination of MTD

Up to six DLT-evaluable patients will be enrolled at DL1 in Part A. If 1 or fewer DLT-evaluable patients experience a Cycle 1 dose limiting toxicity, then DL1 will be the RP2D and up to six additional patients will be enrolled in Part B (PK cohort) at this dose level. If 2 or more patients experience a Cycle 1 DLT at DL1, then the maximum tolerated dose has been exceeded and DL-1 will open for enrollment. Further, if the Part B cohort opens at DL1 and the number of patients in Part A and Part B combined who experience a Cycle 1 dose limiting toxicity exceeds 33%, then the maximum tolerated dose has been exceeded and DL-1 will open for enrollment. Up to six DLT-evaluable patients will be enrolled at DL-1. If 1 or fewer DLT-evaluable patients experience a Cycle 1 dose limiting toxicity at DL-1, then DL-1 will be the MTD/RP2D and up to six additional patients will be enrolled in Part B (PK cohort) at this dose level. If 2 or more patients experience a Cycle 1 DLT at DL-1, then the maximum tolerated dose has been exceeded and the study will close to accrual. Further, if the Part B cohort opens at DL-1 and the number of patients at DL-1 in Part A and Part B combined who experience a Cycle 1 dose limiting toxicity exceeds 33%, then the maximum tolerated dose has been exceeded and the study will close to accrual. See exceptions to rule in Section 11.2.2 for defining the MTD.

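### The uproleselan dosage cell of the Cycle 1-2 Therapy Delivery Map prints 10 mg/kg with no dose-level qualifier, so it is wrong for any patient enrolled at Dose Level -1 (5 mg/kg)

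*Combined protocol and SAP*

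**What the plan says.** Section 5.6 contains a single map headed for Cycles 1-2. On its use it says: "This form is to be completed and uploaded into RAVE at the end of every cycle". In the uproleselan row the dosage column gives a single 10 mg/kg dose on Day 1 and then "Days 2-8: 10 mg/kg Q12H", with a stated total of 15 doses. The row names no dose level and does not point to Section 5.3 or Section 6. Further down, the form has a blank for the assigned dose level and fields for calculated and administered mg.

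The dose itself is set elsewhere. Section 5.3.1 says: "The starting dose will be 10 mg/kg with dose levels for subsequent groups of patients as follows". Table 5 then lists 10 mg/kg as Dose Level 1, marked as the starting level, and 5 mg/kg as Dose Level -1. If the maximum tolerated dose is exceeded at the first level, "then the subsequent cohort of patients will be treated at Dose Level -1". Section 11.3 repeats the rule for its DLT triggers: "then the maximum tolerated dose has been exceeded and DL-1 will open for enrollment".

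Section 6 also allows individual reductions. After a hematological DLT a patient may "proceed to Cycle 2 at the next lower dose level at the discretion of the treating physician and study chair or vice-chair" (Section 6.1.1). After a non-hematological DLT a patient who continues "should receive subsequent doses at the next lower dose level" (Section 6.2.1).

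**The concern.** The dosage column is the part of the form that tells a site what to give. One map serves every patient, and nothing in Section 5.6 limits it to the first cohort. If Dose Level -1 opens, the same form will carry 5 mg/kg in the assigned-level blank and 10 mg/kg in the dosage column.

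The place the map sends the reader for detail does not resolve this. It refers to Section 5.1, but Section 5.1.1 gives the schedule and the infusion time for uproleselan without any mg/kg dose. The reader has to go to Table 5, which the map does not mention.

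What is at stake is agreement between a pediatric dosing form and the dose-level table, in the one situation where the trial has concluded that 10 mg/kg is too much for these patients with this backbone.

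**Working it through.** **Inputs**
- Printed dose: 10 mg/kg on Day 1 and on Days 2-8 (Section 5.6, uproleselan row).
- Schedule: one dose on Day 1, then every 12 hours on Days 2-8 (Sections 5.1.1 and 5.6).
- Dose levels: Dose Level 1 = 10 mg/kg; Dose Level -1 = 5 mg/kg (Table 5).

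**Step 1. Reproduce the plan's dose count.**
Doses per cycle = 1 + 2 × 7 = 15. This agrees with the total in the map and in Section 5.1.1.

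**Step 2. Amount per cycle.**
Amount = dose per administration × 15.
- As printed: 10 × 15 = 150 mg/kg.
- At Dose Level -1: 5 × 15 = 75 mg/kg.
- Difference: 150 − 75 = 75 mg/kg. Ratio: 150 / 75 = 2.

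**Step 3. Who is affected?**

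| Patient | Dose under Table 5 and Section 6 | Dosage cell | Agreement |
|---|---|---|---|
| Dose Level 1, no reduction | 10 mg/kg | 10 mg/kg | yes |
| Enrolled at Dose Level -1 | 5 mg/kg | 10 mg/kg | no, factor 2 |
| Dose Level 1, reduced after a DLT | 5 mg/kg from the reduction on | 10 mg/kg | reduction not shown |

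The second line is the point made here. The third is secondary. The map also leaves out the Section 6 reductions for the other drugs, namely the 50% cut in Cycle 2 high-dose cytarabine for low creatinine clearance (Section 6.3.2.1) and the fludarabine adjustments in Table 7. Leaving dose modifications to Section 6 is the form's general practice.

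**Step 4. Does anything else on the form qualify the cell?**
In part. The assigned-level blank and the mg fields tell the site that a level applies, and Section 3.9 has OPEN assign that level at enrollment. They supply the right level but do not change the printed 10 mg/kg.

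**The case against.** The strongest reply is that dose level is a state of the study, assigned centrally, and that the form treats it that way. OPEN assigns the level and gives the site a printable confirmation with treatment information (Sections 3.8 and 3.9). The form has its own blank for the level and asks for a patient-specific mg dose. It is uploaded at the end of each cycle and is classed as a research record (Section 14.1), while the dose levels are set in Section 5.3. Dose Level -1 is a contingency, and Section 2.5.2 considers it unlikely that DLTs will determine the recommended dose. In adults, 10 mg/kg is the recommended dose, and no DLT was seen up to 20 mg/kg (Section 2.3.2).

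Most of this stands, and it is why the practical risk is low. It does not make the cell correct. Sections 6.1.1 and 6.2.1 themselves speak of a patient starting at Dose Level -1, so such patients are foreseen. Adult tolerability is limited comfort here, because Dose Level -1 opens only after 10 mg/kg has been judged too toxic in this trial. Some safeguards detect an error only afterwards: source verification is retrospective and annual (Section 14.4), and central-monitoring documents are due within two weeks of the time point or cycle (Appendix II).

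A reader might also infer that the map breaks its own convention, since the intrathecal, fludarabine and high-dose cytarabine rows are all printed by tier under "Age-based dosing". The documents support this only weakly. Section 4.1.2 requires age of at least 1 year, and the fludarabine and high-dose cytarabine tiers split at 1 year by age at enrollment (Sections 5.1.2 and 5.1.3). Each of those drugs therefore has one applicable dose in this trial. Only the two intrathecal rows have several tiers in use, and age tiers apply to different patients at the same time, unlike a dose level assigned at enrollment.

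**Conclusion.** The point holds as a minor internal inconsistency in one cell. For a patient enrolled at Dose Level -1, the dosage cell contradicts Table 5 and Section 11.3 and shows twice the intended dose (150 against 75 mg/kg over a full 15-dose cycle). It has no effect for a Dose Level 1 patient without a reduction, and none on sample size, decision rules or analysis. The figures assume that all 15 doses are given.

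Two stronger readings are not supported. A reader might infer that children will be overdosed. The documents give no basis for a probability of error, and several cues point to the right dose: OPEN assignment, the assigned-level blank, the mg fields, and the PK worksheets, which record dose in mg/kg and in mg. A reader might also count the missing Section 6 step-down as a separate defect of equal weight, but it follows the form's practice for the other systemic drugs.

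**What to change.** Change the uproleselan dosage cell only. For both Day 1 and Days 2-8, replace the printed 10 mg/kg with: *assigned dose level per Table 5 (DL1: 10 mg/kg; DL-1: 5 mg/kg), or as reduced per Section 6*.

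Leave the assigned-level blank as it is. Turning it into a level-for-this-cycle field would lose the record of the level assigned at enrollment, and a single entry per cycle could not show a reduction made partway through the cycle.

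The new wording uses only doses already in Table 5. If a Dose Level 2 is later added, which the text under Table 5 leaves open, the amendment that changes the table should update the list in the cell. The cost is one wording edit at the next amendment, with no change to design, sample size or analysis.
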